Obtain demographic data, medical history, medication list, history of drug reactions, personal and family hx of acne/rosacea; perform complete skin exam; obtain standard digital photos of face, chest, and back; count baseline number of macules/papules/pustules on face, chest, and back; obtain optional nasal swab culture

Administer FACT-EGFRI-18 questionnaire

Randomly assigned 1:1

Initiate cetuximab, erlotinib, panitumumab, afatinib or osimertinib therapy Initiate topical triamcinolone 0.1% cream

Initiate cetuximab, erlotinib, panitumumab, afatinib or osimertinib therapy

At any time point, if grade 2 or greater rash develops, initiate treatment as deemed necessary, such as topical steroids or oral antibiotics. Participants will still be followed for the six week duration of study.

incidence and severity

Skin exam. di

Adverse side effects assessment, FACT-EGFRI-18, review of patient diary incidence and severity
Adverse side effects assessment, FACTEGFRI-18, review of patient diary

nt of rash

Week 4

Skin exam, digital photos, assessment of rash

Week 6

Skin exam, digital photos, assessment of rash incidence and severity
Adverse side effects assessment, FACT-EGFRI-18, review of patient diary; obtain optional nasal swab

Week 4

Skin exam, digital photos, assessment of rash

Week 6

Skin exam, digital photos, assessment of rash incidence and severity

Adverse side effects assessment, FACT-EGFRI-18, review of patient diary; obtain optional nasal swab

STUDY SUMMARY

Title	A Randomized Phase II Study of Topical Steroids as Preemptive Therapy for Epidermal Growth Factor Receptor Inhibitor-Induced Papulopustular Eruption		
Short Title	A Study of Topical Steroids as Preemptive Therapy EGFR Inhibitor- Induced Papulopustular Eruption		
Version	07-02-2019		
Study Design	Randomized Control Trial		
Study Center(s)	Robert H. Lurie Cancer Center		
Objectives	To determine the efficacy of preemptive treatment with topical steroids (triamcinolone 0.1% cream for application to face, chest and back) when administered concomitantly for 6 weeks with erlotinib, cetuximab, panitumumab, afatinib or osimertinib to prevent papulopustular eruptions.		
Sample Size	84		
Diagnosis & Key Eligibility Criteria	Patients must have a histologically or cytologically confirmed cancer diagnosis for which EGFRI treatment is indicated, and must be starting treatment with cetuximab, erlotinib, panitumumab, afatinib or osimertinib.		

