3.2 Exclusion Criteria

- 3.2.1 Patients who have used systemic or topical steroids within 7 days of trial registration, or start systemic or topical steroids for reasons unrelated to trial during the 6-week follow up period. Systemic steroids as part of chemotherapy regimen are allowed.
- 3.2.2 Patients who have used antibiotics within 7 days of trial registration, or start antibiotics for other conditions during the 6-week follow up period
- 3.2.3 History of allergic reactions to topical steroids
- 3.2.4 Patients with any rash at the time of study registration
- 3.2.5 Uncontrolled intercurrent illness including, but not limited to, ongoing or active infection, symptomatic congestive heart failure, unstable angina pectoris, cardiac arrhythmia, or psychiatric illness/social situations that would limit compliance with study requirements.

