9.3 Data Analyses Plans

The primary objective will be to assess and compare the incidence of rash in patients treated preemptively with topical steroids and control patients.

Proportions experiencing EGFRI-induced papulopustular eruption (any severity) by 6 weeks will be estimated and compared using the Mantel-Haenszel Chi-Square test to account for the stratification factor in the randomization procedure. A test for homogeneity will be performed to assess the adequacy of a common odds ratio (OR). Results will be summarized using an OR and 95% confidence interval. Supportive analysis will use a generalized estimating equations (GEE) approach, which will allow modeling of the proportion of patients with rash over time. Fixed factors for treatment group, time and the treatment group by time interaction will evaluate time differences in the proportion of patients with rash between the two treatment arms while accommodating repeated measures over time.

The secondary objective, maximum grade severity during the 6-week study period will be tabulated by treatment group and compared using the Cochrane Armitage test for trend.

Secondary endpoints will also include comparisons across the study arms to assess changes in quality-of-life scores from baseline, as measured by the FACT-EGFRI-18 questionnaire. FACT-EGFRI-18 scores will be presented as the median percentage from baseline. Scores at 6 weeks will be compared using the nonparametric Van Elteren test, which combines stratum-specific Wilcoxon Rank-Sum statistics with weights inversely proportional to stratum sizes. Differences in adherence to chemotherapy treatment over the 6 weeks will be compared across the two study arms using the Mantel-Haenszel Chi-Square test. The incidence of adverse events will also be compared across treatment arms with a Fisher exact test.

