Appendix 1: FACT-EGFRI-18 Questionnaire³³ Subject ID number:

	ct ID number:	Date:				
		Not at all	A little bit	Somewhat	Quite a bit	Very much
ST4	My skin or scalp feels irritated	0	1	2	3	4
ST5	My skin or scalp is dry or "flaky"	0	1	2	3	4
ST6	My skin or scalp itches	0	1	2	3	4
ST7	My skin bleeds easily	0	1	2	3	4
ST9	I am bothered by a change in my skin's sensitivity to the sun	0	1	2	3	4
ST32	My skin condition interferes with my ability to sleep	0	1	2	3	4
ST22	My skin condition affects my mood	0	1	2	3	4
ST17	My skin condition interferes with my social life	0	1	2	3	4
ST24	I am embarrassed by my skin condition	0	1	2	3	4
ST37	I avoid going out in public because of how my skin looks	0	1	2	3	4
ST26	I feel unattractive because of how my skin looks	0	1	2	3	4
ST34	Changes in my skin condition make daily life difficult	0	1	2	3	4
ST38	The skin side effects from treatment have interfered with household tasks	0	1	2	3	4
ST16	My eyes are dry	0	1	2	3	4
ST15	I am bothered by sensitivity around my fingernails or toenails	0	1	2	3	4
ST29	Sensitivity around my fingernails makes it difficult to perform household tasks	0	1	2	3	4
B5	I am bothered by hair loss	0	1	2	3	4
ST11	I am bothered by increased facial hair	0	1	2	3	4

NU Study Number: JNC06142016 Other Study Numbers: STU00203631; NU 16D05

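### Summarising FACT-EGFRI-18 as a percentage from baseline fails for patients who start at or near zero on the printed item codes; absolute change in points should replace it

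*Combined protocol and SAP*

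**What the plan says.** The quality-of-life paragraph in section 9.3 names three quantities in turn.

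- It announces "comparisons across the study arms to assess changes in quality-of-life scores from baseline, as measured by the FACT-EGFRI-18 questionnaire".
- It fixes the presentation: "FACT-EGFRI-18 scores will be presented as the median percentage from baseline".
- It fixes the test: "Scores at 6 weeks will be compared using the nonparametric Van Elteren test", stratified as in the randomisation.

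Objective 2.2.2 and endpoint 6.3.2 both concern the difference between arms in how quality of life changes. Section 9.3 plans no between-arm estimate or confidence interval for this questionnaire.

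Appendix 1 prints the instrument: 18 items, each worded as a complaint (for example "My skin or scalp feels irritated"), coded from 0 for not at all to 4 for very much. It gives no rule for forming a total, no direction for the total, and no treatment of missing items. The schedule in section 5.0 places the questionnaire at baseline and weeks 2, 4 and 6. Section 3.2.4 excludes "Patients with any rash at the time of study registration".

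**The concern.** A percentage from baseline needs a baseline well away from zero. On the printed codes, zero is the score of a patient with nothing to report, and a prevention trial that admits only rash-free patients can be expected to enrol some people at or close to that value. For a patient at 0 the stated summary cannot be calculated. For a patient at 1 or 2 it reflects the small denominator more than the size of the worsening. The measure is also lopsided: on the printed codes improvement stops at -100%, while worsening has no comparable limit.

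At stake is the size of the quality-of-life effect as it will be reported. Because the percentage is the only planned description of change, an analyst who meets zero baselines would have to choose after seeing the data whether to omit those patients, assign them a value, or switch measure.

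**Working it through.** The plan gives no expected FACT-EGFRI-18 baseline, standard deviation, effect or power, so there is no stated figure to reproduce. The check is how the prescribed summary behaves on the printed scale.

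**Inputs.** 18 items coded 0 to 4 (Appendix 1); rash-free entry (3.2.4); 42 patients per arm, 84 in total (9.2). The 9-point worsening is illustrative.

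**Range of the raw sum.** 18 × 0 = 0 to 18 × 4 = 72.

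**Percentage change** = 100 × (week 6 − baseline) / baseline. The reversed column uses 72 minus the raw sum for both scores.

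| Raw baseline | Change in points | Percentage, codes as printed | Percentage, total reversed |
|---|---|---|---|
| 0 | 9 | 9/0, undefined | −9/72 = −12.5% |
| 1 | 9 | 9/1 = +900% | −9/71 = −12.7% |
| 5 | 9 | 9/5 = +180% | −9/67 = −13.4% |
| 20 | 9 | 9/20 = +45% | −9/52 = −17.3% |

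A patient who starts and stays at 0 gives 0/0, also undefined. The absolute change is 9 points in every row under either direction; only its sign depends on the direction.

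**How many patients start at 0.** The documents do not say. Assume, purely for illustration, that each item is non-zero at baseline with probability q, independently of the others. Then P(baseline = 0) = (1 − q)^18:

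- q = 0.02: 70%, about 58 of 84
- q = 0.05: 40%, about 33 of 84
- q = 0.10: 15%, about 13 of 84
- q = 0.20: 2%, about 2 of 84

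Items on one questionnaire are correlated in practice, so this shows only how wide the uncertainty is. Per arm, an assumed share of 10% to 40% is 0.10 × 42 ≈ 4 to 0.40 × 42 ≈ 17 patients without a value.

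**Does the median rescue it?** In part. If any worsening from 0 is ranked above every finite percentage, the median stays finite until about half of an arm is in that position. The 0/0 patients still need a rule, and the plan has none.

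**The case against.** The strongest reply is that little depends on this sentence. The formal comparison uses week-6 scores, which exist for every patient with a week-6 form whatever the baseline. This stands. A reader might infer that the quality-of-life p-value, or the trial's main result, is compromised; the documents do not support that.

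Second, freedom from rash is not a score of zero. Appendix 1 also asks about dryness, itch, eyes, nails and hair (for example "I am bothered by hair loss"). Participants are cancer patients, some of them on chemotherapy. Criterion 3.1.2 lets study treatment start within 7 days of the EGFR inhibitor, and section 1.1 places sensory disturbance in weeks 0 to 1. This stands too. A reader might infer that most patients start at 0, but no figure in the documents shows it.

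Third, the instrument's own scoring may reverse the items, in which case a symptom-free patient starts at 72 and nothing is divided by zero. The documents neither state nor exclude this. The point is therefore conditional on the printed codes. It also shows that the summary is not fully specified, because its value depends on an unstated convention.

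Fourth, a reader might infer that the plan drops zero-baseline patients, so that the summary no longer represents those randomised. The text does not say so; it is silent. Dropping them is one of several choices open to the analyst.

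Finally, the phrase could mean the median score as a percentage of the median baseline. That version fails only if the median baseline is 0, but the wording does not settle which is meant.

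None of these replies gives a reason to prefer the percentage. Absolute change is defined for every patient with both scores, under either direction, and is what the paragraph's opening announces.

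**Conclusion.** The concern holds in a limited form. On the item codes as printed, the prescribed summary is undefined at a baseline of 0 and unstable just above it: the same 9 points runs from +45% to +900% as the baseline falls from 20 to 1. Rash-free entry makes low baselines plausible, but their number is unknown.

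The conclusion rests on two assumptions: that the total is formed from the printed codes without reversal, and that at least some patients enter with few or no complaints. If the total is reversed, the division problem disappears and what remains is the unstated scoring rule, plus a summary that still does not match the tested quantity.

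The consequence is confined to how the effect on one secondary endpoint is described. It is worth correcting because that description is the only planned summary of change for objective 2.2.2. It is not a threat to the trial's inference.

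**What to change.** Replace the presentation sentence in section 9.3 with: FACT-EGFRI-18 results will be presented by arm as the median (interquartile range) absolute change from baseline in points, scored by the instrument's scoring rule with the direction stated, with a between-arm difference in points and a 95% confidence interval stratified by skin type (for example, of Hodges-Lehmann type). Drop the percentage. The direction should be taken from the instrument's scoring rule and not inferred from the item codes in Appendix 1.

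Preferably, also apply the Van Elteren test to the same change score, so that summary, test and objective 2.2.2 refer to one quantity.

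The cost is one sentence, or two with the change to the test. No new data are needed, since the questionnaire is already scheduled at baseline and week 6. The presentation change leaves the planned test as it is. Moving the test to the change score has one trade-off to weigh: if baseline and week-6 scores are only weakly correlated, it may be less sensitive than testing week-6 scores. The choice should therefore be made before outcome data are examined.

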4.2 Treatment Administration

4.2.1 Treatment arm: Triamcinolone 0.1% Cream

Eligible patients will be randomly assigned to either the treatment group to receive topical triamcinolone 0.1% cream for application to the face, chest and back, or will be assigned to the control group to receive no preemptive treatment. Patients will be assigned to either group in a randomized manner, stratified according to Fitzpatrick skin type. Stratification group 1 will consist of patients with Fitzpatrick skin type I-III. Stratification group 2 will consist of patients with Fitzpatrick skin type IV-VI. The Fitzpatrick skin typing test is a numerical classification schema for human skin color, as explained below (Fitzpatrick TB. The validity and practicality of sun reactive skin types i through iv. 1988. Archives of Dermatology. 124(6):869-871.)

• Type I (scores 0–6) always burns, never tans (pale white; blond or red hair; blue eyes; freckles)

NU Study Number: *JNC06142016* Other Study Numbers: STU00203631; NU 16D05

- **Type II** (scores 7–13) usually burns, tans minimally (white; fair; blond or red hair; blue, green, or hazel eves)
- **Type III** (scores 14–20) sometimes mild burn, tans uniformly (cream white; fair with any hair or eye color)

- Type IV (scores 21–27) burns minimally, always tans well (moderate brown)
- Type V (scores 28–34) very rarely burns, tans very easily (dark brown)
- Type VI (scores 35–36) Never burns, never tans (deeply pigmented dark brown to darkest brown)

If the patient is randomized to the treatment group, then the study team has the option to distribute the study drug either in person during a clinic visit or by shipping the study drug to the patient after success registration. If shipping the study drug to the patient, then we will use a courier such as FEDEX that provides tracking information and overnight shipments are preferred. The packaging will be secure and tamper proof, and the patient's name and address information will be verified.

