4.3 Toxicity Management & Dose Delays/Modifications

Any patient who receives at least one dose of study therapy will be evaluable for toxicity endpoints. Any patient who develops any of the side effects listed in section 8.1.9 will be taken off of treatment with triamcinolone cream, but will be followed through the study for six weeks.

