4.5 Duration of Therapy

Patients will receive treatment for 6 weeks. If any patient is in the control arm and develops a papulopustular rash, they will be treated with topical triamcinolone 0.1% cream and or antibiotic treatment, oral doxycycline 100 mg or oral minocycline 100 mg twice daily, as is the standard of care. These participants will still be followed for the 6 week duration of study.

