7.2 Definitions & Descriptions

7.2.1 Adverse Event

An adverse event (AE) is any untoward medical occurrence in a patient receiving study treatment and which does not necessarily have a causal relationship with this treatment. Because AEs associated with EGFR- inhibitor treatment are monitored by the treating oncology physician, for the purposes of this study, only AEs that were possibly, probably, or definitely related to triamcinolone 0.1% cream will be collected, including those symptoms listed in section 8.1.9 will be reported. An AE can therefore be any unfavorable and unintended sign (including an abnormal laboratory finding), symptom, or disease temporally associated with the use of an experimental intervention, whether or not related to the intervention.

Recording of AEs should be done in a concise manner using standard, acceptable medical terms. In general, AEs are not procedures or measurements, but should reflect the reason for the procedure or the diagnosis based on the abnormal measurement. Preexisting conditions that worsen in severity or frequency during the study should also be recorded (a preexisting condition that does not worsen is not an AE). Further, a procedure or surgery is not an AE; rather, the event leading to the procedure or surgery is considered an AE.

If a specific medical diagnosis has been made, that diagnosis or syndrome should be recorded as the AE whenever possible. However, a complete description of the signs, symptoms and investigations which led to the diagnosis should be provided. For example, if clinically significant elevations of liver function tests are known to be secondary to hepatitis, "hepatitis" and not "elevated liver function tests" should be recorded. If the cause is not known, the abnormal test or finding should be recorded as an AE, using appropriate medical terminology (e/g/ thrombocytopenia, peripheral edema, QT prolongation).

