7.3 Adverse Event Reporting

7.3.1 Routine Reporting

All routine adverse events that are determined to be possibly, probably, or definitely related to study treatment should be reported on the adverse event (AE) Case Report Form (CRF) within NOTIS Routine AEs will be reviewed by the Data Monitoring Committee (DMC) according to the study's phase and risk level, as outlined in the DSMP.

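### The Fisher test of adverse-event incidence in 9.3 compares arms whose routine adverse events are recorded under different rules

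*Combined protocol and SAP*

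**What the plan says.** The analysis plan (9.3) closes with a between-arm safety test: "The incidence of adverse events will also be compared across treatment arms with a Fisher exact test". It names no analysis population, event set or time window for it.

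Two sections determine which routine events reach the database. Section 7.2.1 explains that EGFR-inhibitor events "are monitored by the treating oncology physician", and that for this study "only AEs that were possibly, probably, or definitely related to triamcinolone 0.1% cream will be collected". The same sentence goes on "including those symptoms listed in section 8.1.9 will be reported". The next sentence of 7.2.1 gives a definition of an adverse event that also takes in unrelated events. Section 7.3.1 sets the case-report-form rule: "All routine adverse events that are determined to be possibly, probably, or definitely related to study treatment should be reported".

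On exposure, 4.2.1 says that patients not given the cream "will be assigned to the control group to receive no preemptive treatment". Section 4.5 adds that controls who develop a papulopustular rash may cross to the drug: "they will be treated with topical triamcinolone 0.1% cream and or antibiotic treatment".

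Section 4.3 says: "Any patient who receives at least one dose of study therapy will be evaluable for toxicity endpoints".

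Section 5.0 schedules adverse-effect assessment, skin exam and diary review at weeks 2, 4 and 6 without distinguishing the arms. Section 7.2.3 collects SAEs whatever their attribution.

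**The concern.** A test of incidence between randomised arms is interpretable only if an event of a given kind has the same chance of being recorded in each arm. Here the entry condition is attribution to the cream, and an event cannot be attributed to a cream that has not been applied. In the steroid arm every patient can contribute from the start. In the control arm a patient can contribute only after developing a rash, and only if the rescue includes triamcinolone rather than an antibiotic alone. Randomisation does not protect a comparison whose recording rule depends on a post-randomisation outcome.

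At stake is a misleading safety statement: an apparent excess of skin events on the steroid that reflects recording. This is prophylaxis given to patients without a rash at entry, so harm relative to no treatment matters to anyone deciding whether to adopt it.

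**Working it through.** **Which rule governs recording.** The broad definition in 7.2.1 says what counts as an adverse event. The collection sentence in 7.2.1 and the form rule in 7.3.1 say what is written down, and both restrict routine events to related ones. Section 7.3.1 refers to study treatment rather than naming triamcinolone. The clause on 8.1.9 symptoms sits inside the relatedness-limited sentence and does not clearly extend collection to untreated controls.

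**Can control capture be worked out?** No. Section 4.5 triggers rescue at any papulopustular rash, the schema at grade 2 or greater. Rescue may omit triamcinolone, and events before rescue remain unattributable. The 75% control rate in 9.2 does not state a grade. Capture has to be varied.

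**Inputs.** From the plan: 42 per arm (9.2) and two-sided 5% (Study Summary). The plan gives no figure for the adverse-event test. Its sample size, the source of the 42, reproduces for 45% versus 75%:

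[1.96·√(2·0.60·0.40) + 0.842·√(0.45·0.55 + 0.75·0.25)]² / 0.30² = (1.358 + 0.555)² / 0.09 ≈ 40.7, so 41 per arm. With 42 per arm, power is 81.3%.

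Assumed, not in the documents: a true risk q of a qualifying event that is equal in both arms, full recording in the steroid arm, and a fraction c of control events recorded.

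**Formula.** Recorded counts are X_T ~ Bin(42, q) and X_C ~ Bin(42, q·c). The rejection probability is the sum of P(X_T=a)·P(X_C=b) over all (a, b) with two-sided Fisher p≤0.05.

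**Threshold when no control events are recorded.** For k events against 0, p = 2·C(42,k)/C(84,k).
- k=5: 2·850,668/30,872,016 = 0.055
- k=6: 2·5,245,786/406,481,544 = 0.026

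Six recorded steroid-arm events (6/42 = 14%) are therefore enough. At c=0 the rejection probability is P(X_T≥6).

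**Chance of p≤0.05 with no true difference:**

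| True risk q | c=0 | c=0.25 | c=0.50 | c=0.75 | c=1 |
|---|---|---|---|---|---|
| 5% | 1.7% | 1.1% | 0.7% | 0.5% | 0.5% |
| 10% | 24% | 11% | 5% | 2% | 2% |
| 20% | 87% | 44% | 18% | 6% | 3% |
| 30% | 99% | 71% | 30% | 8% | 3% |

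If only 75% of steroid-arm events are attributed and recorded, the c=0 column falls to 9% at q=10% and 93% at q=30%.

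**Events that resemble the eruption.** Section 8.1.9 lists pimples, itching, crusting and redness. If such items were recorded in both arms and simply tracked the eruption at the planned 45% versus 75%, the same enumeration gives p≤0.05 with probability 77%, essentially always in favour of the steroid. Tested together with the other signs, they would largely repeat the efficacy comparison.

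**The case against.** The strongest reply is that this is loose wording rather than a broken comparison. Section 7.2.1 contains a definition that includes unrelated events, 7.1 follows patients with events whatever the relationship to drug, both arms are assessed at every visit, and the 8.1.9 symptoms are said to be reported. This shows that the text is inconsistent and that much of the information may be seen at visits. It does not override the collection and form rules, and assessing an event is not the same as recording it.

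A second reply is that the size is driven by assumption. That stands. At a 5% risk, plausible for signs such as skin thinning, even zero control capture gives no inflation above 5%. At 75% capture the distortion is small. Equal true risk is also doubtful for eruption-like items, which could be commoner in controls and pull the other way.

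Three stronger readings are tempting and not supported:
- A reader might infer that control events are zero by design. They are not, because 4.5 allows triamcinolone rescue.
- A reader might infer that 4.3 removes controls from the safety population. That sentence gives a sufficient condition without saying that it is the only one, and study therapy is undefined. Both arms follow a protocol skin regimen, so controls may count. Section 4.3 adds only an ambiguity.
- A reader might infer that the trial's conclusions are at risk. Adverse-event incidence is not a listed objective, and 9.3 attaches no decision rule to the test.

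**Conclusion.** The concern holds for routine adverse events. As written, the 9.3 test compares arms under different recording rules, and control capture depends on rash and on rescue choice, so a recorded difference cannot be read as a difference in harm. SAEs (collected regardless of attribution), FACT-EGFRI-18 and the primary endpoint are outside the problem.

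The documents do not fix its size. Under equal true risks and full steroid-arm capture, the distortion ranges from none at a 5% risk to near-certain false significance at a 30% risk with no control capture, and it is modest once about three quarters of control events are captured. The case for change rests on the recording rule, not on any one of these figures. It should be corrected, but it does not threaten the main result.

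**What to change.** **Minimum.** In 9.3, drop the between-arm Fisher test for attributed routine adverse events and report them descriptively among patients exposed to triamcinolone. This is one sentence and needs no new data.

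**If a between-arm comparison is wanted.** Amend 7.2.1, 7.3.1 and 9.3 so that the 8.1.9 symptoms are recorded in both arms regardless of attribution at the existing week 2, 4 and 6 reviews. Compare all randomised patients over the same 6 weeks. Keep items that overlap the papulopustular eruption separate and descriptive.

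In either case, define study therapy in 4.3 so that the status of controls is clear.

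The cost of the fuller version is slightly more data entry, mainly for controls, and some signs will be harder to judge at remote visits. Power for rare signs is low: for a true 10% versus 0% it is P(X_T≥6) = 24%, so a non-significant result should not be read as evidence of safety.
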